In our pilot study of 91 community-dwelling postmenopausal women of European ancestry treated with 2300-2500 IU of vitamin D₃ daily for 4-6 months, we utilized novel liquid chromatography, tandem mass spectroscopy (LC-MS/MS) methodology to evaluate serum levels of cholecalciferol (vitamin D₃) and 24,25(OH)₂D at baseline and after 4-6 months. We observed the anticipated relationship with cholecalciferol: a greater increase in circulating vitamin D₃ is associated with a greater increment in 25(OH)D. Additionally, we reproduced the observation of others [Wagner et al., 2011] that a higher ratio of 24,25(OH)₂D/25(OH)D after supplementation is associated with a less robust increase in 25(OH)D. Thus, our pilot work supports the premise that smaller increments in 25(OH)D may result from relatively low vitamin D₃ input (presumably from poor absorption) and/or greater degradation. To this end, we performed multiple regression analysis to determine the characteristics that might enable prediction of the 25(OH)D achieved with supplementation. The equation from the final model was: post-treatment 25(OH)D = 8.3 + (1.05*baseline 25(OH)D) – (7.7*baseline 24,25(OH)₂D) + (0.53*follow-up cholecalciferol) + (4.2*follow-up 24,25(OH)₂D). This model had an adjusted $R^2 = 0.55$ with $p < 0.001$ for all the parameters, thus accounting for approximately half of the variance in the final 25(OH)D level. The baseline values of cholecalciferol could not be used in this model because the data were highly skewed (virtually all values were zero since the assay is currently not capable of measuring very low concentrations of cholecalciferol). Nonetheless, these preliminary data support the dosing algorithm described below.

HYPOTHESES AND SPECIFIC AIMS

Aim 1:

Determine the efficacy of our dosing algorithm in achieving total 25(OH)D concentrations of 35-50 ng/mL in women of European and African ancestry.

To validate our vitamin D₃ dosing algorithm, we will conduct a randomized, double-blind, controlled, six-month duration clinical trial of daily oral vitamin D₃ to determine the efficacy of dosing following our algorithm compared to 2500 IU/day (control arm) in achieving the target total 25(OH)D concentration of 35-50 ng/mL. Participants will be community-dwelling post-menopausal women of European and African ancestry, who have a baseline total serum 25(OH)D of ≥ 10 but < 30 ng/mL.

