H1a: The percent of individuals with total 25(OH)D of 35-50 ng/mL will be significantly higher in the dosing algorithm arm than in the control arm.

H1b (exploratory aim): The percent of African ancestry women with total 25(OH)D of 35-50 ng/mL will be similar to (i.e., not significantly different than) that in women of European ancestry.

Aim 2:

Determine additional factors that predict response to vitamin D supplementation.

We will expand our predictive model to include baseline serum cholecalciferol and body composition, measured by dual-energy x-ray absorptiometry (DXA), and genotypes in the *GC* and *CYP2R1* genes. In exploratory analyses we will also determine the effect of self-reported ancestry on our dosing algorithm.

H2a: Baseline body mass, but not total body fat, will be negatively associated with total 25(OH)D after supplementation, indicating that individuals with larger body size, not just body fat, will require a higher dose of vitamin D₃ to attain the target total 25(OH)D range.

H2b: Baseline cholecalciferol will be positively associated with 25(OH)D after supplementation, where individuals with higher values will require a lower dose.

H2c: There will be a negative association between the number of risk alleles in the two genes and total 25(OH)D after supplementation, where individuals with more risk alleles will require a higher dose.

Completion of these aims will allow us to validate and refine our vitamin D dosing algorithm. This predictive tool will allow clinical estimation of the dose needed to achieve a target 25(OH)D level, advancing clinical care by allowing personalization of vitamin D supplementation. Moreover, the insight gained from the proposed study will enable clinical trials of other vitamin D-related outcomes to achieve more effective vitamin D supplementation by using our dosing algorithm. This will enhance future research proposals by radically improving the study design.

STUDY DESIGN

Study Design and Population.

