$(7.7 \times \text{baseline } 24,25(\text{OH})_2\text{D}) + (0.53 \times \text{follow-up cholecalciferol}) + (4.2 \times \text{follow-up } 24,25(\text{OH})_2\text{D})$. Using only the baseline values, which would be available at an initial clinical visit, including baseline cholecalciferol, $\text{post-treatment } 25(\text{OH})\text{D} = 18.19385 + (0.65967 \times \text{baseline } 25(\text{OH})\text{D}) + (1.02393 \times \text{baseline } 24,25(\text{OH})_2\text{D}) + (0.13564 \times \text{baseline cholecalciferol})$. For the current study, the dosing at both baseline and the 3-month follow-up visit will be determined using this equation to predict post-treatment 25(OH)D (at the 3-month follow-up visit, the 3-month values will be substituted for the baseline values in the equation). Specifically, for those whose predicted 25(OH)D is ≥ 35 ng/mL and < 50 ng/mL, we will administer a dose of 2500 IU daily. For those whose predicted 25(OH)D is < 35 ng/mL, we will administer 4000 IU/day and for those whose predicted 25(OH)D is > 50 ng/mL we will administer 1000 IU/day. The target 25(OH)D range was selected as nearly all experts agree that 25(OH)D levels above ~ 30 - 32 ng/mL are adequate; hence we have chosen a target level ≥ 35 ng/mL to account for assay variability, thereby assuring that all have concentrations > 30 - 32 ng/mL. An upper limit of 50 ng/mL was selected based on evidence suggesting that 25(OH)D levels above this value might have adverse effects [Sempos et al., 2013; Stolzenberg-Solomon et al., 2010]. All three of the daily doses are within the range considered to be safe by a recent Institute of Medicine report [Ross 2011].

INCLUSION/EXCLUSION CRITERIA

Inclusion criteria:

- Healthy, community-dwelling postmenopausal woman (natural menopause, 12 consecutive months without menstruation, or surgical menopause and \geq age 55, or surgical menopause and postmenopausal symptoms \geq 12 months ago)
- Self-reported $> 50\%$ European or $> 50\%$ African ancestry
- Able and willing to sign informed consent as affirmed by research staff person obtaining consent
- Screening serum 25(OH)D concentration of 10.0-29.9 ng/mL
- Willing to not alter the amount of their baseline vitamin D supplementation during the course of this study
- Willing to use sunscreen (SPF ≥ 15) when sun exposure of > 15 minutes is expected during the months of May through September

Exclusion criteria:

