In the primary analyses for Aim 1 (H1a), treatment group (control versus dosing algorithm) will be the independent variable; for H1b, ancestral group (European versus African ancestry) will be the independent variable and only individuals in the dosing algorithm group will be included. For both H1a and H1b, the dependent variable will be the percent of individuals with a 25(OH)D concentration of 35-50 ng/mL at the three- and six-month follow-up visits. A two-sample test for binomial proportions will be used. We will also determine the effect of treatment group and ancestry on free (bioavailable) 25(OH)D concentration using an analysis of variance.

The control group will be used as an unbiased external validation of our dosing algorithm, in which we will repeat the multiple regression analysis in the control sample and compare the coefficients to those in our original equation. In Aim 2 (H2a-c), we will further develop our dosing algorithm by determining if baseline serum cholecalciferol, baseline body composition, and genotypes in the *GC* and *CYP2R1* genes are associated with response to vitamin D₃ supplementation. In exploratory analyses we will include two-way interaction terms between ancestry and each of our primary predictors to determine if the effect of any of these biologic predictors varies by ancestral group.

Sample Size Justification.

For H1a, the outcome variable will be the percent of individuals with a 25(OH)D concentration of 35-50 ng/mL at the three- and six-month visits. Based on our preliminary data, we expect 40% of the individuals receiving 2500 IU/day to achieve 25(OH)D of 35-50 ng/mL. We expect our dosing algorithm to increase this to at least 55%, a conservative estimate. We calculated the sample size required in each arm to detect this difference with power of 80% and a one-sided significance level (α) of 0.05. A sample of 167 participants in each arm, decremented to 150 by a 10% loss to follow-up will be required.

In the multiple regression models for H2a-c, with a total sample size of 150 from the control arm, an α of 0.05, and power of 80% we would be able to detect a factor that accounts for as little as 8% of the variation in 25(OH)D concentration after vitamin D supplementation.

Multisite Conduct Plan

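### H1a is defined at both the 3- and 6-month visits but sized as one test; with no primary visit or combining rule, its error rate and power are not fixed in advance.

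*Combined protocol and SAP*

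**What the plan says.** Statistical Methods gives the dependent variable for H1a as the percent of women with 25(OH)D of "35-50 ng/mL at the three- and six-month follow-up visits. A two-sample test for binomial proportions will be used". Sample Size Justification says the same: "the outcome variable will be the percent of individuals with a 25(OH)D concentration of 35-50 ng/mL at the three- and six-month visits".

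The sizing itself is for one comparison. The control rate is introduced with "Based on our preliminary data, we expect 40% of the individuals receiving 2500 IU/day to achieve 25(OH)D of 35-50 ng/mL", the algorithm arm is expected to reach at least 55%, and the level appears only here: "We calculated the sample size required in each arm to detect this difference with power of 80% and a one-sided significance level" of 0.05. The result is 167 women per arm, reduced to 150 by 10% loss to follow-up.

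The hypothesis adds no time point. H1a says only that the percent in range "will be significantly higher in the dosing algorithm arm than in the control arm". Aim 1 describes the trial's length: "we will conduct a randomized, double-blind, controlled, six-month duration clinical trial". Vitamin D Preparation and Dosing says that "the dosing at both baseline and the 3-month follow-up visit will be determined using this equation", with the 3-month values replacing the baseline values on the second occasion.

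No section says which visit is primary, how two visits become one result, or how the level is shared if both are tested.

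**The concern.** Two visits and one test leave the primary analysis undefined. At least three rules are possible:

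- a test at each visit, with either success counting;
- a test at each visit, with both required;
- one result per woman, in range at both visits.

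These rules have different false-positive rates and different power, and the stated 5% and 80% do not hold under all of them. Because the plan does not choose, the choice could be made after results are seen.

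The visits also answer different questions. Month 3 reflects only the first algorithm dosing decision, while month 6 follows both.

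**Working it through.** **Inputs from the documents.** Rates 40% and 55%, one-sided 0.05, power 80%, 10% loss (Sample Size Justification); 1:1 allocation (Study Design and Population).

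**Assumptions.** The correlation between the two visits is not given, so 0.3 to 0.9 is shown. The two-visit calculations take 40% vs 55% at each visit.

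**Step 1: reproduce the stated size.** With mean rate 0.475 and difference 0.15:

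n = [1.645 × √(2 × 0.475 × 0.525) + 0.842 × √(0.40 × 0.60 + 0.55 × 0.45)]² / 0.15² = 136.0

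Continuity correction: (136.0/4) × [1 + √(1 + 4/(136.0 × 0.15))]² = 149.03, so 150. Loss: 150/0.9 = 166.7, so 167. Both match the plan. The two-sided 0.05 equivalents are 173, or 186 with correction, which do not match. The stated size is therefore that of one test at the full one-sided 0.05.

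**Step 2: one named visit, 150 per arm.** Error 5%. Power = Φ{[0.15 − 1.645 × √(0.49875/150)] / √(0.4875/150)} = Φ(0.967) = 83.3%. With continuity correction the difference becomes 0.15 − 1/150, and power is Φ(0.850) = 80.2%.

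**Step 3: a test at each visit, one-sided 0.05.** Treat the two test statistics as bivariate normal with correlation r.

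- Either counts: error = 1 − P(Z3 < 1.645, Z6 < 1.645).
- Both required: power = P(Z3 < b, Z6 < b), with b = 0.967, or 0.850 with continuity correction.

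| r | Either counts: error | Both required: power (with correction) |
|---|---|---|
| 0.3 | 9.3% | 71.6% (67.0%) |
| 0.5 | 8.8% | 73.4% (69.1%) |
| 0.7 | 8.0% | 75.6% (71.6%) |
| 0.9 | 6.8% | 78.9% (75.3%) |

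With both required, error is 0.7-3.2% if neither visit has an effect. It rises to about 5% if only one visit has an effect, since one true null must then be rejected at 0.05. The correct statement is at most 5%.

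**Step 4: in range at both visits, per woman.** This is one test, so error is 5%. If 40% and 55% are both-visit rates, Step 1 applies unchanged. If they are per-visit rates, the both-visit rate is p² + ρp(1 − p), where ρ is the within-woman correlation:

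- ρ = 0.3 in both arms: 23.2% vs 37.7%, power 86.3% (83.3% with correction).
- ρ = 0.9 in both arms: 37.6% vs 52.5%, power 83.2% (80.1%).
- ρ = 0.6 control, 0.5 algorithm: 30.4% vs 42.6%, power 71.2% (66.9%).
- ρ = 0.5 control, 0.6 algorithm: 28.0% vs 45.1%, power 92.7% (90.8%).

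Power under this reading then rests on a quantity the plan does not give.

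**Step 5: which rate is 40%?** Background says the pilot measured serum levels "at baseline and after 4-6 months. We observed the anticipated relationship with cholecalciferol". That suggests one follow-up measurement, and so a single-visit rate. This is an inference: the documents do not show how the 40% was obtained.

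**The case against.** The strongest reply is that the text already defines one outcome. It says three- *and* six-month, names one test, and gives 40% and 55% directly after that definition. On their face these are the rates for being in range at both visits, in which case there is one result per woman, error is 5% and 150/167 is right. This largely stands. It is the closest literal reading, and nothing in the documents excludes it. What it lacks is a statement that the rates are both-visit rates, and the apparent single follow-up in the pilot gives reason to ask.

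Three further objections have weight. First, no passage says that success at either visit suffices. Second, if the rates are per-visit and the within-woman correlation is the same in both arms, both-visit power stays at about 80% or above. The unequal-correlation cases only show sensitivity. Third, Statistical Methods states no level. If the two tests were two-sided at 0.05, the either-visit error in favour of the algorithm would be 3.5-4.8%. Single-visit power would then be 74.2% (70.3% with correction), so the 80% claim would fail instead.

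A reader might infer more than the documents support:

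- **That the trial's false-positive rate is inflated.** Inflation arises only if either visit counts, or if both visits are pooled as independent observations: 1 − Φ(1.645/√(1 + r)), or 7.5% at r = 0.3 and 10.4% at r = 0.7. The plan states neither rule.
- **That the sample size is wrong.** The arithmetic is right for one test.
- **That the interim analysis adds further error.** The Data and Safety Monitoring Board section mentions an interim analysis of results but describes no efficacy stop, so none is counted here.

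**Conclusion.** The concern holds as a gap in the definition of the primary analysis, not as a demonstrated error. The stated 5% and 80% are both secured under one named visit, or under an in-range-at-both outcome whose rates really are 40% and 55%. Running the stated test at each visit loses one or the other: error of 6.8-9.3% if either counts, or power of 67-75% with continuity correction (72-79% without) if both are required.

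The ranges rest on an assumed between-visit correlation of 0.3-0.9 and on equal rates at the two visits. The second assumption is a simplification, because the algorithm acts once before month 3 and twice before month 6. That the 40% is a single-visit rate is inferred, not stated. This is a cheap improvement, held with moderate confidence.

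**What to change.** In Statistical Methods and Sample Size Justification, name month 6 as the single primary time point for H1a and state that it is tested at the one-sided 0.05 used for sizing. Month 6 is the end of the treatment period and the only visit that follows both algorithm dosing decisions. Make month 3 secondary, tested only if month 6 succeeds, so that the order of testing protects the 5% level.

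This takes a few sentences and no extra participants, and keeps 150/167 per arm with about 80% power. The cost is that month 3 can no longer carry the primary claim and the outcome narrows from two visits to one.

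If being in range at both visits is what is meant, say so and confirm that 40% and 55% are both-visit rates. That needs one sentence and no change in size. If they are not, give the expected both-visit rate in each arm and restate the power, which could change the sample size.

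Keeping two separate tests costs more. With continuity correction, splitting the level (one-sided 0.025 each, either counting) and sizing each test for 80% power needs 186 evaluable and 207 randomized per arm. Requiring both tests to succeed needs 192 to 168 evaluable (214 to 187 randomized) per arm for correlations of 0.3 to 0.9.

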Vitamin D deficiency is associated with many adverse health outcomes and is much more prevalent in individuals of African ancestry than in those of European ancestry. Treatment of vitamin D deficiency in both clinical and research settings has focused on the administration of a fixed dose of vitamin D. However, the increase in circulating 25-hydroxyvitamin D (25[OH]D) in response to a fixed dose is highly variable from person to person [Aloia et al., 2008; Binkley et al., 2011], yet little is known about the determinants of this inter-individual variation. Our preliminary data suggest two factors, baseline total 25(OH)D and 24,25(OH)₂D (an indicator of 25(OH)D degradation), explain a significant amount of this variation. We have developed an algorithm that uses these factors to tailor the vitamin D₃ dose administered. **The next step and primary goal of this proposal is to validate the algorithm in an independent sample of post-menopausal women of European and African ancestry. Additionally, we will examine the following novel factors that may contribute to the remaining inter-individual variability in response to vitamin D supplementation:** serum levels of cholecalciferol (vitamin D₃; absorption), body composition (storage), and genes coding for the vitamin D binding protein (*GC*; transportation) and 25 hydroxylase (*CYP2R1*; synthesis) [Engelman et al., 2013]. Our rationale for the proposed research is that validation and refinement of our dosing algorithm would optimize vitamin D supplementation and potentially improve downstream health outcomes.

BACKGROUND

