Potential volunteers will be screened by telephone. Those meeting all inclusion and no exclusion criteria will be invited to a screening study visit. At screening, informed consent will be obtained. We will then collect the following to determine study eligibility: basic demographic information (age, ancestry, and education); medical history; medication and supplement use; and blood for screening 25(OH)D and calcium tests. If a subject is not eligible for study participation based on 25(OH)D value, her screening serum calcium sample will not be run, and the sample will be destroyed. Additionally, these subjects will be notified if their ineligibility was due to their 25(OH)D value being too high or too low for study requirements. This will occur starting with subjects who are screened from the time of Amendment 1's IRB approval. All subjects with screening 25(OH)D within ± 5 ng/mL of the range noted above, and offer permission, may be contacted to re-screen at a future time point. Volunteers meeting all inclusion and no exclusion criteria will be invited to participate and complete a study baseline visit, at which point they will be considered enrolled. At baseline, participants will be randomly assigned to the control or dosing algorithm group. Both participants and study staff who have contact with the participants will be blinded to group assignment. Follow-up visits will occur at three and six months. At baseline and follow-up visits, height and weight will be measured, and blood will be drawn for the vitamin D panel, calcium, and PTH. Blood for DNA extraction and body composition will only be obtained at the baseline visit. Participants will be asked to return all unused study supplements and compliance will be assessed at each follow-up visit by pill count. Safety will be monitored through adverse event reporting and review of calcium results. Study visits are summarized in the flow chart below.

Study Visit Event Flow Chart

Time	-1	0	3	6
Study visit	Screening	Baseline	3-month	6-month
Informed consent	X			
Demographic information	X			
Medical history	X			
Medication and supplement use	X	X	X	X
Serum 25(OH)D	X			
Serum calcium	X	X	X	X
Height and weight measurement		X	X (weight only)	X (weight only)
Body composition measurement		X		
Whole blood for DNA extraction		X		
Serum vitamin D panel		X	X	X
Serum free 25(OH)D and 1,25(OH) ₂ D		X	X	X
Plasma calcium and PTH		X	X	X
Randomization		X		
Supplement dispensation and accountability		X	X	

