An assay to directly measure free serum 25(OH)D is currently nearing completion of development in [name] lab and will be used for the proposed study in year 2 or 3. Evidence on the importance of free 25(OH)D is evolving; it is important to measure this to enable us to incorporate it into our analytic plan. Serum 1,25(OH)₂D will also be measured in [name] lab by LC-MS/MS to fully characterize vitamin D status. Serum (at screening) and plasma (all other visits) calcium will be measured in the UW Clinical Laboratory to assess potential vitamin D toxicity. Plasma PTH will be measured using commercially available kits in [name] laboratory as a surrogate of the physiologic effect of vitamin D.

Genotyping of Vitamin D-related Genetic Variants.

Genotyping will be performed at the using the University of Wisconsin DNA Sequencing Facility using the KASPar® assay system from KBiosciences, Ltd (Hoddesdon, UK). We will genotype a non-synonymous (coding) SNP, rs4588, in *GC* that results in an amino acid change in the vitamin D binding protein, affecting its metabolism, [Kawakami et al., 1981] blood concentration [Lauridsen et al., 2001], and affinity for 25(OH)D [Arnaud and Constans, 1993]. This SNP, or a SNP in strong linkage disequilibrium (correlation) with this SNP, is associated with 25(OH)D in multiple studies [Ahn et al., 2010; Engelman et al., 2008; Engelman et al., 2013; Lasky-Su et al., 2012; Lu et al., 2012; Robien et al., 2013; Wang et al., 2010; Zhang et al., 2012]. We will also genotype a SNP, rs2060793, in *CYP2R1*.

This SNP, or a SNP in strong linkage disequilibrium with this SNP, has also been associated with 25(OH)D in multiple racial/ethnic groups [Ahn et al., 2010; Engelman et al., 2013; Lasky-Su et al., 2012; Robien et al., 2013; Wang et al., 2010; Zhang et al., 2012]. [name] is co-leading the TRANS-ethnic Evaluation of vitamin D (TRANSCEND) consortium, a multi-study collaborative effort to combine existing genome-wide association data from ethnic/racial minority populations with measured 25(OH)D. This consortium currently includes 6,765 individuals of African ancestry. Through this collaborative effort, [name] may become aware of additional SNPs that are relevant in individuals of African ancestry. If this occurs, these additional SNPs will be genotyped.

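### The free 25(OH)D analysis names no visit and leaves out the scheduled baseline value, so the arm comparison loses precision and the ancestry contrast shows achieved levels only

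*Combined protocol and SAP*

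**What the plan says.** The whole analysis of free 25(OH)D is one sentence in Statistical Methods, which says that the study will "determine the effect of treatment group and ancestry on free (bioavailable) 25(OH)D concentration using an analysis of variance". The outcome is a concentration and the factors are arm and ancestry. The sentence does not say whether the outcome is the 3-month value, the 6-month value or a change, and it lists no covariate. Baseline predictors enter only the separate Aim 2 regressions.

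In the Study Visit Event Flow Chart, the row beginning "Serum free 25(OH)D" is marked at the baseline, 3-month and 6-month visits. Additional Laboratory Analyses says of this measurement that "it is important to measure this to enable us to incorporate it into our analytic plan". No other section adds a baseline term to the analysis.

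**The concern.** A two-factor analysis of variance of a follow-up concentration ignores a covariate that the study already plans to measure. Two things follow.

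- **Arms.** These are randomised, so leaving out baseline does not bias the comparison. It widens the confidence interval.
- **Ancestry.** This is not randomised. A difference at follow-up combines where the women started with how they responded, and the model has no term to tell the two apart. A reader of a reported ancestry effect may take it for a difference in response.

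Because no visit is named, the choice between month 3, month 6, both, or a change score would also be open once the data are in hand.

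**Working it through.** **The plan's own figure.** No power or sample size is stated for free 25(OH)D. The only figure available is the one for H1a in Sample Size Justification: 40% against 55%, one-sided 0.05, 80% power. The two-proportion formula gives 136 per arm without continuity correction and 150 with it, and 150/0.9 = 167. The stated 150 and 167 are reproduced, and 150 per arm is used below.

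**Arm comparison.** Let r be the correlation of baseline with follow-up free 25(OH)D within arm and ancestry groups. The protocol gives neither r nor an SD, so r is assumed to be 0.3 to 0.7 and results are in SD units.

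- Detectable difference without baseline (two-sided 0.05, 80% power): (1.960 + 0.842) × √(2/150) = 0.323 SD.
- With baseline as covariate, the residual variance is multiplied by 1 − r², and the detectable difference by √(1 − r²).
- Number per arm that would give the same precision without adjustment: 150/(1 − r²).

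| r (assumed) | Variance ratio 1 − r² | Variance reduction | Detectable difference (SD) | Power at 0.323 SD | Equivalent n per arm |
|---|---|---|---|---|---|
| none used | 1.00 | – | 0.323 | 80% | 150 |
| 0.3 | 0.91 | 9% | 0.309 | 84% | 165 |
| 0.5 | 0.75 | 25% | 0.280 | 90% | 200 |
| 0.7 | 0.51 | 51% | 0.231 | 98% | 294 |

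**Where r may lie.** The baseline-only equation in Vitamin D Preparation and Dosing has a coefficient of 0.66 on baseline total 25(OH)D. This suggests that baseline carries forward, but it concerns total 25(OH)D and is not a correlation. Two design features point to a lower r. Eligibility restricts the range of total 25(OH)D. In the algorithm arm, dose also runs opposite to the predicted level: with the other terms at zero, a prediction of 35 ng/mL corresponds to a baseline of (35 − 18.19)/0.660 = 25.5 ng/mL, and women predicted below 35 receive the larger dose.

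**Ancestry contrast, for illustration only.** Assume about 150 evaluable women per ancestry (167 × 0.9), equal SDs, and no ancestry difference at follow-up once baseline is given. A baseline gap of d SD then appears at follow-up as r × d, and is declared significant with probability Φ(rd/√(2/150) − 1.96) + Φ(−rd/√(2/150) − 1.96).

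| Assumed gap d | r = 0.3 | r = 0.5 | r = 0.7 |
|---|---|---|---|
| 0.2 SD | 0.06 SD, 8% | 0.10 SD, 14% | 0.14 SD, 23% |
| 0.5 SD | 0.15 SD, 25% | 0.25 SD, 58% | 0.35 SD, 86% |

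These would be false findings only if the result were read as a difference in response. As statements about achieved level they would be true differences.

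**Site and ancestry in one model.** The variance of the ancestry term is inflated by 1/(1 − c²), where c is the site–ancestry correlation. For an assumed c of 0.8 this is 1/0.36 = 2.8, and for 0.9 it is 1/0.19 = 5.3. The largest gain from baseline adjustment in the first table is 1/0.51 = 2.0, so entering both could leave the ancestry term less precise than before.

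**The case against.** The strongest reply concerns ancestry. A reader might infer that the unadjusted ancestry contrast is biased. The documents do not support that. The sentence speaks of an effect on concentration, not on response, and H1b likewise compares achieved levels. A difference in achieved level is a legitimate descriptive quantity.

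Nor do the documents show that a baseline gap in free 25(OH)D exists among enrolled women. The introduction says that deficiency "is much more prevalent in individuals of African ancestry than in those of European ancestry", but that describes populations and vitamin D status in general. Both groups must also meet "Screening serum 25(OH)D concentration of 10.0-29.9 ng/mL", which limits any gap in the total. That window does not constrain free 25(OH)D, so a gap remains possible, but its size and direction are unknown. What stands is narrower: the contrast cannot separate starting level from response, and calling it an effect invites the wrong reading.

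A second reply is that the plan is silent on baseline rather than opposed to it. That is so, but silence on both visit and covariates leaves the analysis undefined.

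A third is that the gain is uncertain and the outcome minor. Both are fair. At r = 0.3 the saving is only 9% of the variance, and the 51% figure should not be presented as the likely one. Free 25(OH)D appears in no numbered hypothesis and has no power calculation.

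**Conclusion.** The point holds as a precision and definition problem in a supporting analysis. The visit is not named, and a baseline value that is already scheduled is not used. The arm comparison stays unbiased; its variance could be 9% to 51% lower for r between 0.3 and 0.7, with reasons to expect the lower part of that range. The range rests wholly on an assumed correlation.

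For ancestry, the conclusion is one of interpretation: the planned contrast is a difference in achieved level. Baseline adjustment would not make it causal. Analysis of covariance and change-score answers can differ when non-randomised groups start apart, and error in an assay that Additional Laboratory Analyses describes as still being completed would leave the adjustment incomplete.

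H1a, its test and its sample size are not affected.

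**What to change.** Replace the sentence in Statistical Methods with one that states the following:

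1. **Outcome.** Free 25(OH)D at 6 months, or months 3 and 6 jointly in a mixed model.
2. **Model.** Analysis of covariance (or the mixed model) on treatment group and ancestry, with baseline free 25(OH)D as covariate.
3. **Arm comparison.** Include site as a stratification factor.
4. **Ancestry.** Report the term as a baseline-adjusted association, not an effect, alongside the unadjusted difference in achieved level. Add site to this contrast only if the two ancestries overlap enough within sites. Study Design and Population treats site and ancestry as one stratification factor, and the Amendment 5 summary says that each site can now enrol both groups, so the two may still be nearly collinear. Tabulate site by ancestry before unblinding to settle this.

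The cost is a few lines of text. No new visit or sample is needed, because the baseline measurement is already in the flow chart.
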